10.3.3 OL-300 Analyses

The following values of the additional immunological parameters will be summarized using descriptive statistics overall and for each age group, visit and time point in total and by initial actual treatment group (placebo/dose level/overall active) on the OLS-300.

- Absolute values at Month 0, Month 12, last value prior to switch to Viaskin Milk 300 μ g and all scheduled visits in the analyzed OL-300 period
- Changes from last value prior to any active treatment
- Changes from last value prior to switch to Viaskin Milk 300 μ g

10.4 ACCIDENTAL CONSUMPTION OF COW'S MILK

10.4.1 General

Accidental consumption of cow's milk is reported on a specific forms in the CRF, containing frequency, description of reaction(s) (if any) and medication(s) (if any).

10.4.2 Double-blind Month 12 and OL-500 analyses

Frequency of accidental consumption of cow's milk (in any form) was summarized overall and for each age group, in total and by treatment group (placebo/dose level/overall active) on the SS during the randomized blinded treatment period.

Number of allergic reactions and use of treatment for allergic reactions resulting from presumed accidental consumption of cow's milk, were summarized overall and for each age group in total and by treatment group (placebo/dose level/ overall active) on the SS during the randomized blinded treatment period.

Same descriptions were performed overall and for each age group, in total and by initial actual treatment group on the OLS-500 for the Viaskin Milk 500 μ g open-label treatment period.

The quantity of food consumed, details of symptoms and treatment of allergic reaction were presented in listings. Adverse events corresponding to these accidental consumption of cow's milk were listed.

This document is confidential

Statistical Analysis Plan

10.4.3 OL-300 Analyses

Frequency of accidental consumption of cow's milk protein (in any form) will be summarized overall and for each age group, in total and by initial actual treatment group (placebo/dose level/overall active) on the OLS-300 in the analyzed OL-300 period.

Number of allergic reactions and use of treatments for allergic reaction resulting from presumed accidental consumption of cow's milk, will be summarized overall and for each age group in total and by initial actual treatment group (placebo/dose level/ overall active) on the OLS-300 in the analyzed OL-300 period.

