1.1 Background

Food allergies represent a major health problem that can affect up to 6% of young children and 3 to 4% of adults, and appears to have an increasing prevalence.^{1,2} Allergic reactions to food can result from different immunologic mechanisms including immunoglobulin E (IgE)-mediated reactions (acute onset), non-IgE cell-mediated reactions (delayed or chronic onset) or a combination of both. Food allergies lead to a large variety of clinical symptoms involving the skin, and/or the gastrointestinal and respiratory tracts, and the cardiovascular system. Of these food allergy symptoms, those described as anaphylactic shock can be life-threatening and require a rapid admission to an emergency room.

Cow's milk allergy (CMA) is the most common food allergy in infants and young children, with an incidence of approximately 2 to 3% in developed countries.^{3,4} Several studies have shown that the prognosis for developing tolerance to cow's milk is good, with a majority of patients outgrowing their CMA by the age of 2 to 3 years.^{5,6} However, other studies have shown that tolerance might also occur much later, with an increasing number of children whose CMA persists into school age and even into adolescence.⁷ Recent studies suggest that the resolution rate of CMA is approximately 50% by 5 years of age.^{8,9} The low levels of allergen-specific IgE (sIgE) to cow's milk and milk skin prick test (SPT) wheal size have been shown to be good predictors of resolution, while high levels of cow's milk sIgE have been shown to be predictors of persistence of CMA.¹⁰ The concomitant presence of both asthma and allergic rhinitis, and the severity of atopic dermatitis have also been shown to be associated with a lower likelihood for developing tolerance.¹¹

To date, the standard of care for management of food allergy is strict avoidance of the responsible allergen(s). This is especially challenging for cow's milk, which is widely included in many dairy products, and also in smaller amounts in other manufactured food products. Consequently, the risk of accidental allergic reactions in children allergic to cow's milk represents a major health concern, and the frequency of accidental exposure, some leading to severe reactions, could reach 40% in children over a 12-month period.¹¹

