9.3.4.3 Subject-Year Analysis

Analysis by subject-year will be performed for the OLS-300 equivalently as described in [Section 9.3.3.3](#):

- a) The treatment durations and the respective AEs of subjects randomized to Placebo or Viaskin Milk 150 μ g in the DB-period will be assigned to the treatment arm "Placebo" or "Viaskin Milk 150 μ g", respectively.
- b) The treatment durations and the respective AEs of subjects randomized to Viaskin Milk 300 μ g in the DB-period and the whole OL-300 period will be added to the treatment arm "Viaskin Milk 300 μ g".

This document is confidential

Statistical Analysis Plan

- c) The treatment durations and the respective AEs of subjects randomized to Viaskin Milk 500µg in the DB-period and the whole OL-500 period will be added to the treatment arm "Viaskin Milk 500µg".

These treatment durations in days will be divided by 365.25 to get the subject-years. The number of AEs will be divided by the respective subject-years.

9.4 SYMPTOMS ELICITED DURING THE DBPCFC.

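### Accidental milk consumption and its reactions are tabulated without time at risk, so the final OL-300 and OL-500 tables cannot be read against the 12-month blinded table or the protocol's annual background figure

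*SAP*

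**What the plan says.** SAP 10.4.3 defines two summaries for the open-label 300 µg period. The first covers how often milk was taken by accident: "milk protein (in any form) will be summarized overall and for each age group, in total and by initial actual treatment group". The second is "Number of allergic reactions and use of treatments for allergic reaction resulting from presumed accidental consumption of cow's milk, will be summarized overall". Both are split by initial actual treatment group on the OLS-300.

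SAP 10.4.2 gives the same summaries for the blinded period, where consumption of cow's "milk (in any form) was summarized overall and for each age group, in total and by treatment group", "on the SS during the randomized blinded treatment period". For OL-500 it adds: "Same descriptions were performed overall and for each age group, in total and by initial actual treatment group on the OLS-500". Protocol 8.1.8 also asks only for a frequency, together with circumstances, quantity and reactions. Neither document asks for a rate per unit of time in this analysis.

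The SAP does use person-time elsewhere. Section 9.3.4.3 states: "The number of AEs will be divided by the respective subject-years". That analysis, and the one in 9.3.3.3, cover the adverse event overview parameters and events by system organ class and preferred term. Accidental consumption is not among them. It is recorded on its own form (SAP 10.4.1).

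**The concern.** The periods differ in length, so the same underlying risk gives different frequencies in different tables. A reader of the final report will have the blinded, OL-500 and OL-300 tables side by side. There will also be the protocol's background figure, which is annual: the frequency of accidental exposure "could reach 40% in children over a 12-month period" (Protocol 1.1). A crude frequency over about 24 months cannot be set against either a 12-month table or an annual figure.

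The endpoint is exploratory, but it bears on a stated aim. Protocol 1.4 lists, among the goals of developing the product, protection from severe reactions when a child is accidentally exposed. After Month 12 there is no concurrent placebo group, and the OL-300 food challenges are optional. Accidental exposures are therefore among the few efficacy-related observations that do not depend on willingness to be challenged. The plan also does not relate reactions to reported consumptions, which is the simplest way to separate fewer exposures from better tolerance of each one.

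**Working it through.** The documents give no computed figure for this endpoint, so there is nothing to reproduce. What follows illustrates how period length alone changes the tables.

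**Inputs**

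- Blinded period: 12 months (SAP 3.1).
- OL-500: variable, up to 36 months (SAP 3.1). The exposure classes in SAP 9.1.2 start at 0 to 6 months.
- OL-300, final analysis: SAP 6.2.2 assigns accidental consumption from VS1 (excluded) to VS6/VS7, about 24 months. The Year 1 analysis stops at VS3/VS4, about 12 months.
- Annual risk p of at least one exposure: 40% is the protocol's upper background figure. Values of 10% and 20% are assumed, to show a range.

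**Formulas.** With a constant hazard, λ = −ln(1 − p) per year. The share with at least one event by t years is 1 − (1 − p)^t. Expected events per 100 subjects are 100·λ·t.

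| Annual risk | λ per year | Share, 12 mo | Share, 24 mo | Difference | Events per 100, 12 mo | Events per 100, 24 mo |
|---|---|---|---|---|---|---|
| 10% | 0.105 | 10.0% | 19.0% | +9 points | 10.5 | 21.1 |
| 20% | 0.223 | 20.0% | 36.0% | +16 points | 22.3 | 44.6 |
| 40% | 0.511 | 40.0% | 64.0% | +24 points | 51.1 | 102.2 |

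Both readings of frequency are shown because the SAP does not say whether it means subjects with an event or events.

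**Sensitivity at 40%**

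- Subjects differ in risk (gamma frailty with variance v). Let l = ((1 − p)^(−v) − 1)/v; the share at t is 1 − (1 + v·l·t)^(−1/v). For v = 1, l = 0.667 and the 24-month share is 57.1% (+17 points). For v = 2, l = 0.889 and it is 53.1% (+13 points).
- Dropout of a fraction d, spread evenly over the 24 months. The share is (1 − d)·0.64 plus d times the average of 1 − exp(−λu) for u from 0 to 2, which is 0.374. For d = 10%: 0.576 + 0.037 = 61.3% (+21 points). For d = 30%: 0.448 + 0.112 = 56.0% (+16 points). Events per 100 are 97.1 and 86.8, against 51.1 in the blinded year.

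**A real benefit.** If the true rate halves in OL-300, the 24-month share is 1 − exp(−0.511 × 0.5 × 2) = 40.0%, and expected events are 51.1 per 100. Both equal the blinded-year values, so the improvement would be invisible.

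**OL-500.** At 40%, a subject followed for 6 months has a 22.5% chance of at least one event; at 36 months it is 78.4%. The mean duration is not given, so the direction of the distortion is not known.

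**With person-time.** An unchanged risk gives the same expected rate in every period: 0.511 per subject-year at 40%, 0.223 at 20% and 0.105 at 10%.

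**The case against.** The strongest reply is that nothing planned is harmed. The endpoint is exploratory, the tables are descriptive within each period, and no test of open label against the blinded year, or against the background figure, is planned. This stands. The harm is misreading across tables, not a false formal conclusion.

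A second reply is that rates already cover the serious events. Systemic adverse events of special interest, and events leading to epinephrine, are in the overview list of SAP 9.3.3.1, which feeds the subject-year analyses. This is partial cover: those events are not split by milk ingestion, so the tables in 10.4 are not repaired.

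A third is that a reader could derive the missing measures. Exposure duration is summarized per period (SAP 9.1), and consumptions and reactions are tabulated on the same sets. If frequency counts events, reactions per consumption follow by division. That is partly right, but the SAP does not define frequency in this way. The table mock-ups are separate documents and cannot be checked. A hand calculation would also give no interval that allows for repeat events in a subject.

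A reader might infer more than the documents support:

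- That an unchanged risk will look like a large rise throughout open label. The OL-300 Year 1 table covers about the same length as the blinded year, and OL-500 can be biased in either direction.
- That comparisons between arms are distorted. The blinded period is nominally 12 months in every arm. Nothing shows that open-label duration differs by arm: the switch depended on regulatory approvals and site supply (Protocol 3.1).
- That 24 points is the expected size. It rests on an upper background figure and a constant, common hazard.

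**Conclusion.** The concern holds for the final OL-300 table and for OL-500, as a weakness of descriptive reporting. Without time at risk, neither table can be compared with the blinded year or with the annual background figure. For the final OL-300 table, period length alone would add about 9 to 24 points to the share with at least one exposure for annual risks of 10% to 40%. At 40%, frailty or dropout brings the 24 points down to between 13 and 21. Event counts would double with complete follow-up, and would be 1.7 to 1.9 times as high with 30% to 10% dropout (86.8/51.1 and 97.1/51.1).

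These figures assume an unchanged rate and full follow-up in the blinded year. The risks are background or assumed values, not trial results. The point that the periods are not comparable does not depend on them. Because the endpoint is exploratory and the remedy is cheap, this is a worthwhile reporting improvement and not a threat to the trial's main conclusions.

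**What to change.** In SAP 10.4.3 add, by period and treatment received:

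- subject-years, counted over the same window that assigns the events;
- accidental consumptions per subject-year and reactions per subject-year, each with a 95% confidence interval that allows for repeat events in a subject (for example, from a negative binomial model);
- reactions per reported consumption.

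Use the subject-year approach of 9.3.3.3 and 9.3.4.3, and state whether frequency means subjects or events. In the final report, show the same rates for the blinded and OL-500 periods as supplementary columns beside the existing counts.

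No new data are needed: SAP 6.2.2 already assigns consumptions to periods by date, and period dates and exposure durations are defined. The cost is SAP wording and a modest amount of extra descriptive analysis of an exploratory endpoint. Section 10.4.2 describes analyses already run, so the added rates for the blinded and OL-500 periods would be post hoc and should be labelled so.

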10.5 RISK TAKING BEHAVIORS

10.5.1 General

Deliberate consumption is defined as cow's milk consumption documented on the accidental cow's milk consumption form, which is not confirmed to be accidental.

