7.3.2.12 Subject Diary Cards

Diary cards will be dispensed to the subjects at Visit 4 and as needed during the study. At each subsequent visit after Visit 4, the diary card will be reviewed by appropriate personnel at the site and the data in the card will be collected for entry into the eCRF or into the clinical database.

Subjects or their parent(s)/guardian(s) will be instructed how to use the diary card from Visit 4 (Day 1) and to bring the card to the site at each subsequent visit. Subjects or their parent(s)/guardian(s) will be instructed to record on their diary cards any AEs/medical events and associated medications, the duration of application and reason for removal of the Viaskin patch, if the patch is removed before the recommended duration in addition to any information regarding cow's milk consumption (including dairy products or any baked milk product) during their participation in the study.

At the clinical site, upon review of the diary cards, the investigative staff will interview the subject to know whether the milk consumption was either accidental or voluntary. This will be useful for the Investigators to assess whether there has been any risk-taking behavior and collect as much information as possible about those cases.

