8.1.8 Exploratory Variables

Exploratory endpoints include the change from baseline value in level of sIgE to peanut, egg, house dust mite, and grass pollen at all timepoints.

Exploratory endpoints will also include the change from baseline in epigenetic modifications at Month 12 and after Month 12 if evaluated.

The above analyses will be defined in the SAP.

Filaggrin gene mutations will be assessed from a blood sample collected at 1 visit and the results will be listed. The relationship between the presence of filaggrin mutations, safety and response to treatment will also be investigated. This analysis will be defined in the SAP.

Exploratory endpoints will also include the enumeration and characterization of reactions triggered by accidental consumption of cow's milk (in any form) and the analysis of "risk-taking behavior" of subjects (or voluntary milk consumption as assessed by the Investigators) during the study. Both pieces of information (accidental consumption and reactions triggered by consumption) will be collected from subject Diary Cards and voluntary or accidental consumption will be assessed by the investigative staff while interviewing the subjects.

Frequency of accidental consumption of cow's milk (in any form), conditions around the accidental consumption, estimated quantity consumed at each occurrence, and associated reactions and severity of reactions will be analyzed separately.

Risk-taking behaviors: frequency of deliberate consumption of cow's milk (in any form), conditions around the consumption, estimated quantity consumed at each occurrence and associated reactions with these consumptions will be analyzed separately. Relatedness to the subject's age category will also be analyzed.

End-of-study surveys completed by the investigators will be analyzed to assess the planned management of each subject after termination of the study.

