10.5.3 OL-300 Analyses

Frequency of deliberate consumption of cow's milk (in any form) will be summarized overall and for each age group in total and by initial actual treatment group (placebo/dose level/overall active) on the OLS-300 in the analyzed OL-300 period.

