12.5 AMENDMENT 5: FINAL VERSION 5.0, 15 MAY 2018

Following study design change implemented in protocol amendment 5, dated 15 May

This document is confidential

Statistical Analysis Plan

2018, to allow all study subjects to switch from Viaskin Milk 500 μ g to Viaskin Milk 300 μ g for a 24 months treatment period, no change between applicable protocol and current SAP version.

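### SAP 10.5.1 counts a milk intake as deliberate unless it is confirmed accidental, whereas the protocol requires staff to have assessed it as voluntary

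*SAP*

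**What the plan says.** Protocol 7.3.2.12 has families note any milk intake on the diary card. When the card is reviewed, "the investigative staff will interview the subject to know whether the milk consumption was either accidental or voluntary". Protocol 8.1.8 repeats that "voluntary or accidental consumption will be assessed by the investigative staff while interviewing the subjects", and describes risk-taking as "voluntary milk consumption as assessed by the Investigators". It asks for accidental and deliberate intake to be analysed separately, and for risk-taking to be related to age category. Both are exploratory endpoints.

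The SAP works from a CRF form instead. Section 10.4.1 says: "Accidental consumption of cow's milk is reported on a specific forms in the CRF". Sections 10.4.2 and 10.4.3 then summarise the frequency of accidental intake, and the reactions and treatments "resulting from presumed accidental consumption of cow's milk". For risk-taking, section 10.5.1 states: "Deliberate consumption is defined as cow's milk consumption documented on the accidental cow's milk consumption form, which is not confirmed to be accidental". Section 10.5.3 applies this to the period still to be analysed: "Frequency of deliberate consumption of cow's milk (in any form) will be summarized overall and for each age group".

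SAP section 12 lists changes from the protocol's analysis, amendment by amendment. This definition is not among them. The entry for Amendment 5 says there is "no change between applicable protocol and current SAP version", and the entry for Amendment 6 reports none.

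**The concern.** The two definitions differ in what they need as evidence. The protocol needs a positive finding that the intake was voluntary. The SAP needs only that confirmation of an accident is absent. A blank answer, or one where staff could not tell, satisfies the second definition but not the first.

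At stake are two descriptive endpoints that are meant to be distinct: reactions to accidental exposure, and risk-taking with its relation to age. If records of unknown intent are placed in the risk-taking table, that table no longer shows only what staff judged to be voluntary. If the same records also stay in the accidental table, the two tables overlap and cannot be read side by side.

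**Working it through.** The documents give no figure for milk intakes or for how often intent is unknown, so there is nothing to reproduce. The check sets the definitions side by side and counts.

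**Where each record goes, on the wording**

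| Record on the form | Protocol 8.1.8 | SAP 10.5 (deliberate) | SAP 10.4 (accidental) |
|---|---|---|---|
| Assessed accidental (A) | accidental | no | yes |
| Assessed voluntary (V) | voluntary | yes | not excluded by any stated rule |
| Intent missing or undetermined (U) | neither | yes | not excluded; presumed accidental could cover it |

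**Count of deliberate intakes**

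- Protocol definition, for records on the form: V.
- SAP 10.5.1: V + U.
- Ratio: (V + U) / V.

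Illustration with assumed counts, 100 form records and V = 5:

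- U = 0: 5 against 5, ratio 1.
- U = 5: 10 against 5, ratio 2.
- U = 15: 20 against 5, ratio 4.

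**Possible overlap of the two tables**, with U = 15 and therefore A = 100 − 5 − 15 = 80:

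- Accidental table takes every form record: 100 + 20 = 120 entries for 100 records.
- Accidental table takes A and U: 95 + 20 = 115 entries.
- Accidental table takes A only: 80 + 20 = 100 entries. There is no overlap, but deliberate is still 20 instead of 5.

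The SAP does not say which of the three applies.

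**Intakes not on the form.** SAP 10.5.1 can count only what is on the accidental-consumption form. Let M be the voluntary intakes that never reach it. Protocol 7.3.2.6 describes that eCRF section in terms of reactions to accidental consumption. SAP 10.4.1 says the form records a reaction only where there was one, so it seems to accept intakes without a reaction, but an intake already recognised as voluntary need not be entered there. Staff-assessed voluntary intakes are then V + M against the SAP's V + U, a difference of U − M. The SAP count is too high if U exceeds M and too low if M exceeds U. Neither is known.

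**The case against.** The strongest reply is that the phrase about confirmation simply refers to the interview result. Staff must ask whether each intake was accidental or voluntary. If the form carries a compulsory two-way answer, whatever is not confirmed accidental is voluntary. Then U = 0, the SAP and the protocol agree, and section 12 has nothing to declare. The CRF is not in the documents, so this cannot be excluded. What remains is that SAP 10.5.1 does not mention the interview and, as worded, settles every unanswered case in one direction.

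Three stronger readings are tempting, and none is supported:

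- **That risk-taking is inflated several-fold.** A reader might assume 5–10% of records voluntary and 10–30% undetermined, and obtain factors from (10+10)/10 = 2 to (5+30)/5 = 7. No such shares are in the documents. Starting the undetermined share at 10% also rules out in advance the case of no effect.
- **That records are counted twice.** The word presumed qualifies only the reaction and treatment counts, not the frequency line, and 10.5.1 can be read as the complement of a confirmed-accidental class. The table shells are separate documents. Overlap is possible but not shown.
- **That the youngest children are misclassified and the age comparison is distorted.** The documents say nothing about how often intent is unknown at any age. Parents or guardians also complete the diary cards, and the SAP's age groups are 2–11 and 12–17, with no toddler group.

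**Conclusion.** The point holds as a defect in the definition. As written, SAP 10.5.1 assigns intakes of missing or undetermined intent to the deliberate class, which is not how protocol 7.3.2.12 and 8.1.8 define risk-taking, and SAP 10.4 has no rule that keeps those records out of the accidental tables.

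The excess among form records is exactly U, which may be zero. The net direction depends on U − M and is unknown. These conclusions rest on the plain wording, without sight of the CRF form or the table shells. The consequence is limited to exploratory, descriptive frequencies with no test attached. The primary analysis is unaffected. It is worth correcting because the OL-300 tables are still described as to be produced and the correction is cheap.

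**What to change.** In SAP 10.4.1 and 10.5.1:

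1. Name the staff interview assessment as the source of the classification.
2. Count as deliberate only intakes assessed as voluntary, and as accidental only those assessed as accidental.
3. State that the classes are mutually exclusive.
4. Show any record with missing or undetermined intent in its own row, by age group (2–11 and 12–17).

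Apply this to the OL-300 tables and record the change in SAP section 12.

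The cost is a few sentences and one table row. The interview is already required, so no new assessment is needed. Whether the CRF separates undetermined from blank should be checked; if it does not, one combined row is enough. The added row goes beyond the protocol's two classes, which is a reason to declare it.

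The downside is comparability. The double-blind and OL-500 tables are reported as already run, under the definition now in 10.5.1. A note should say so, and a supplementary line adding undetermined to voluntary among form records would give the OL-300 figure on the same footing. If U turns out to be zero, the results do not change and only the wording is clearer.
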